capture physiological stress. Most importantly, the supplemental analysis holds the potential to significantly advance the sciences of caregiving, self-management, and biobehavioral health by uncovering unknown associations between race and gender and indicators of heart rate variability from which health disparities related to stress and health may be identified and may inform the future tailoring of health self-management interventions.

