## Special/Vulnerable Populations

1. Indicate specifically if you will include each of the following special populations by checking the appropriate box:

- Adults unable to consent
- Minors (infants, children, teenagers)
- Wards of the state

- Foster Children
- Pregnant Women
- Neonates
- Neonates of Uncertain Viability
- Employees of CWRU or UHHS
- Prisoners

- Illiterate Individuals**
- Non-English Speaking**
- University Students**
- None**

2. If the research involves individuals that are included in a special/vulnerable population, describe the additional safeguards included to protect the rights and welfare of the individuals for each population indicated. *If family caregivers who do not speak/understand the English language come forward with interest in participating and if they meet all other study criteria, we will make accommodations for translating the study measures and intervention materials or for having an interpreter provide appropriate explanations. If an illiterate individual comes forward with interest in participating and if they meet all other study criteria, we will make accommodations to dictate the consent form and all study questions. If a caregiver is an employee or student of CWRU, the consent form identifies participation in this research study is voluntary and if they choose not to participate, it will not affect their current or future relations with the university.*

3. If excluding pregnant women, illiterate or non-English speaking individuals, provide a scientific rationale for the exclusion. Inconvenience or cost is not an acceptable rationale.

*Pregnant women are excluded due to the measure of heart rate variability (HRV). The inclusion of pregnant women has the potential to alter the analyses that involve HRV measurement.*

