Individuals will be assigned a study ID using our enrollment log. In addition, at enrollment we will collect demographic information including age, gender, race, ethnicity, marital status, education, income, occupation, hours of work/week, if the participant is an employee or student at CWRU, health conditions, current medications, relation to person with bipolar, age of family member with bipolar, how many years ago was family member diagnosed with bipolar disorder, specific diagnosis of family member, predominant behavior style of family member with bipolar, whether or not caregiver lives with this family member, whether or not caregiver provides care/assists with basic needs (and how many hrs/day), how many years caregiver has been providing care, if other adults help provide care for family member with bipolar disorder. Some, but not all of the demographic and other questions asked at baseline will also be asked at T2 and T3. We will then proceed with data collection, consisting of surveys to measure bipolar symptoms, caregiver reactions, caregiving involvement, bipolar knowledge, resourcefulness, health risks, and health outcomes. They will also have their heart rate variability (HRV) measured using a non-invasive device on the wrists; it

will take approximately 10 minutes to collect the data. The entire first meeting will take approximately 60-90 minutes. The second and third data collection meeting will be approximately 60 minutes. In the event there is an equipment malfunction or a poor reading is obtained by a research team member, we may need to re-collect the HRV and/or survey data again after a data collection meeting. **COVID-19 modification:** HRV data will not be collected when data collection is done remotely (T2 or T3 only) and will be considered missing data. When we are able to collect HRV data, we will do so by bringing an HRV device to the study participant at a set date and time, providing instructions on how to use the HRV device, safety information on the HRV device, and also providing support via phone or video. HRV data collected this way will be collected for 15-20 minutes instead of 10 minutes, to ensure reliable data is collected. A study team member will collect the HRV device the same day or within 28 hours, at a mutually convenient time. Each HRV device will be sanitized before and after each study participants' use.

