Following the T1 data collection, the project manager will randomize each caregiver into one of four groups using Qminim, a secure online minimization program. Research assistants will be blinded as to which intervention arm caregivers are assigned to. The four groups are: 1) control group- no intervention; 2) usual care group- will receive bipolar education; 3) Self-management (SM)- need based, determined by baseline cut scores from T1- either bipolar education (ED), biofeedback (BF), resourcefulness training (RT), or no need; 4) SM-preference-based, caregiver selects intervention (ED, BF, RT, or no intervention). For SM-need, for example, caregivers scoring <70% on bipolar knowledge would be assigned to ED, < 97 on the resourcefulness scale to RT, and low HRV as determined by SDNN parameter for age and gender to BF. Those in the SM-need and SM-preference groups will perform one SM intervention (as listed above). Those in the usual care group will receive the same bipolar educational intervention as others in the SM-need or SM-preference groups. All interventions will take 4 weeks and these 4 weeks will occur between the T1 and T2 data collections; the T2 data collection is planned to occur 6 months after the initiation of the intervention. The T3 data

we are excluding pregnant women from joining the study (due to the variance in HRV data which would affect scoring for minimization), if someone becomes pregnant while they are enrolled in the study, we will not exclude them from the remainder of the study.

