*Individuals will be encouraged to continue with the interventions if they found them helpful (for BF, caregivers will have been given information on deep-breathing techniques without using a device). Caregivers who cannot be reached by phone or email for follow-up (either intervention or data collection) will have a letter sent to them if they have consented to having a letter sent to their home. Occasionally, calls will need to be made to study participants outside of the office (e.g., evenings/ weekends; when a research team member is working remotely/ in the field) or participants will request to be contacted by text. In these instances, the research team will use Google Voice, which allows users (research team) to set up a phone number through their CWRU email and is connected to their personal mobile phones. Calls and texts can be made to/ from the mobile phones while masking the actual phone number. When the research team is not working, calls will be directed to voicemail.*

*From Modification #8 (approved 03/06/2019)-- At the end of the T3 data collection, study participants will receive a brochure from each of the three interventions being researched, as well as an answer sheet for Caregiver Knowledge of Bipolar Disorder Questionnaire. Study participants who received an intervention will be asked a series of questions (up to 16) about their experience with, and opinion of, the intervention they received. Study participants who have already completed all three data collection sessions and have already agreed to be contacted for any questionnaire follow-up will be called and asked questions over the phone.*

Page 14 of 29

*The supplemental analysis will use baseline data (T1) to explore relationships among caregiver characteristics (race and gender), psychological stress (caregiver reactions and caregiving involvement), and physiological stress (heart rate variability time and frequency domains). De-identified baseline data from the demographic measures, psychosocial measures (caregiver reactions, caregiver involvement) and the HRV measurements will be used for this analysis.*

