caregiving involvement; and **A3**) build caregiver profiles from demographic/contextual factors that are associated with their needs and preferences for the self-management interventions. Accordingly, **A2** will be tested with a series of bivariate analyses including correlations, one way analyses of variance (ANOVA) and independent samples t-tests. We will run correlations when both variables are continuous. If the independent predictor variable is categorical and the dependent outcome is continuous, we will run an ANOVA. When the independent variable is dichotomous and the outcome is continuous, an independent samples t-test will be run. **A3** will build profiles 8 groups from two of the study arms: 1) SM-need and 2) SM-preference. To identify the unique characteristics of each group. Univariate descriptive statistics will be run on the contextual variables within the caregiver, care recipient, and caregiving situation. We will also examine cut points from measures of the self-management processes (knowledge, resourcefulness, and heart rate variability). These analyses will build profiles to show which caregivers may benefit most from a specific self-management intervention. We will prescreen for potential violations of assumptions for correlations. Scatter plots between two variables will identify influential cases, patterns of nonlinearity and constant-error variance that may reduce Parson's  $r$ . To address potential violation of the assumptions, influential cases can be removed. Data transformations can be used to remedy issues such as non-linearity, non-constant error variance, and non-normal error variance. For ANOVAs and t-tests, assumptions of normality and homogeneity of variance will be tested. Non-parametric equivalence tests will be used if assumptions are violated.

For the supplemental analysis, VivoSense software will be used to perform automatic cleaning and computation of heart rate variability measures (SDNN, RMSSD, TP, VLF, LF, HF, LF/HF). Data analysis will consist of descriptive and inferential statistics using SPSS. Description of the sample will include age, gender, race/ethnicity, marital status, education level, annual income, and caregiver relationship. Additionally, descriptive statistics will be calculated for the study measures.

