The aims for the supplemental analysis are to: **SA1**) determine whether there are differences by caregiver characteristics (race and gender) on measures of psychological stress responses (caregiving involvement and caregiver reactions), **SA2**) determine whether there are differences by caregiver characteristics (race and gender) on measures of physiological stress responses (heart rate variability domains), **SA3**) examine associations among indicators of psychological stress responses (caregiver reactions and caregiving involvement) and physiological stress responses (heart rate variability domains, and **SA4**) explore relationships among time and frequency domains of heart rate variability. **SA1** and **SA2** will be tested with a series of independent samples t-tests. **SA3** and **SA4** will be tested with a series of bivariate correlations.

Potential violations of assumptions for correlations and t-test will be assessed. To address violations of the assumptions for correlation, influential cases may be removed. Data transformations may be used to remedy issues such as non-linearity, non-constant error variance, and non-normal error variance. To address violations of the assumptions for t-test, non-parametric equivalence tests will be used if assumptions are violated.

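### Supplemental analysis (SA2, SA3): add age- and gender-adjusted estimates beside the planned unadjusted HRV comparisons, using data already collected at T1

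*Combined protocol and SAP*

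**What the plan says.** The Data Analysis Plan states that SA1 (psychological stress by race and gender) and SA2 (HRV by race and gender) "will be tested with a series of independent samples t-tests". SA3 (stress with HRV) and SA4 (HRV time with frequency domains) "will be tested with a series of bivariate correlations". If assumptions fail, the plan allows transformation or removal of influential cases for correlations, and non-parametric tests in place of t-tests. None of these brings in a covariate.

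The covariates are available. Under Study Design/Procedures, "at enrollment we will collect demographic information including age, gender, race, ethnicity". In the supplemental analysis, age appears only in the sample description: "Description of the sample will include age, gender, race/ethnicity, marital status, education level, annual income, and caregiver relationship".

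Elsewhere the protocol treats participant characteristics as relevant to HRV. The need-based rule in Study Design/Procedures assigns caregivers with "low HRV as determined by SDNN parameter for age and gender to BF" (biofeedback). The Special/Vulnerable Populations section explains one exclusion this way: "The inclusion of pregnant women has the potential to alter the analyses that involve HRV measurement".

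The Background says the supplement may uncover associations of race and gender with HRV "from which health disparities related to stress and health may be identified and may inform the future tailoring of health self-management interventions".

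**The concern.** Race and gender are not randomized, and each is tested alone. If the White and African American caregivers differ in mean age or in the proportion of women, a difference in HRV between them mixes race with age and gender. A correlation between stress and HRV can likewise reflect a third variable related to both.

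For gender, the documents point to both sides of SA3. The Background reports more caregiving time and role strain among women, and the SDNN rule is gender-specific. For age, they point only to the HRV side.

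The stake is interpretation. Someone using a race difference in HRV to tailor an intervention would want to know whether it is seen among caregivers of the same age and gender. The planned output does not say.

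**Working it through.** The documents give no alpha, power, effect size, group split or sample size for SA1 to SA4, so there is no stated figure to reproduce. They give seven HRV measures and a trial target of 360. That target is an upper bound for the supplement, which is limited to White or African American caregivers without an acute respiratory condition. **Every other input below is assumed.**

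**Race contrast in HRV (SA2), through age**
- Shift in the unadjusted difference = (age gap between race groups, in SD) × (age-HRV correlation, absolute value).
- Balanced age: 0. Low end: 0.2 × 0.2 = 0.04 SD. High end: 0.5 × 0.5 = 0.25 SD.
- SE = √(1/(pn) + 1/((1−p)n)), with p the share of the smaller race group. For n = 360, p = 0.3: √(1/108 + 1/252) = 0.115, so the shift is 0.04/0.115 = 0.3 to 0.25/0.115 = 2.2 SE.
- Over p = 0.2 to 0.5, the shift is 0.2 to 1.5 SE at n = 150, 0.25 to 2.0 SE at n = 250 and 0.3 to 2.4 SE at n = 360.

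**Race contrast in HRV, through gender**
- Shift = (difference in gender mix) × (gender difference in HRV). For 0 to 20 percentage points and 0.2 to 0.5 SD: 0 to 0.20 × 0.5 = 0.10 SD.

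**What adjustment does**
- Suppose the race difference at equal age is zero. The unadjusted 95% CI then excludes zero with probability Φ(λ − 1.96) + Φ(−λ − 1.96), where λ = shift/SE. At n = 360 with a 30/70 split this is 6.4% for a shift of 0.04 SD and 58.5% for 0.25 SD.
- Simulation (4,000 runs, same n and split) gave 6.0% and 58.5% unadjusted, against 4.8% and 5.2% from a model with race, age and gender. With no age gap, both were near 5%.
- A second simulation (3,000 runs, gap 0.5, correlation 0.5) fitted age as linear when the true effect was not. Exponential decline: 44.9% unadjusted, 4.9% adjusted. Decline to age 55, then flat: 46.0% and 4.5%.
- Precision: SE ratio (adjusted/unadjusted) = √((1 − r²)/(1 − R²)), with r the age-HRV correlation, d the age gap and R² = p(1−p)d²/(1 + p(1−p)d²). For r = 0.2 to 0.5, d = 0 to 0.5 and p = 0.2 to 0.5, the ratio is 0.87 to 1.01.

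**Stress-HRV correlation (SA3)**
- If the partial correlation is zero, age induces r = (age-stress correlation) × (age-HRV correlation). Taking 0.1 to 0.2 and 0.2 to 0.5: 0.02 to 0.10. With SE = 1/√(n − 1) = 0.053 at n = 360, that is 0.4 to 1.9 SE.
- Taking 0.2 to 0.5 on both sides instead: 0.04 to 0.25. The answer is set by the assumed inputs.
- Gender induces p(1−p)d₁d₂/√((1 + p(1−p)d₁²)(1 + p(1−p)d₂²)), with p now the proportion of men and d₁, d₂ the gender differences in stress and HRV. For 20 to 40% men and differences of 0.2 to 0.5 SD, this is 0.006 to 0.057, at most 1.1 SE at n = 360.

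**Removal of influential cases**
- Simulation with true r = 0 (n = 180 and 360, 4,000 runs; normal, heavy-tailed and skewed data). Type I error was 2 to 7% under four fixed rules: Cook's D > 0.5, Cook's D > 1, |z| > 3 and |studentized residual| > 3. With Cook's D > 4/n it was 9 to 10% in normal data and 4 to 7% otherwise.
- It became large only when three cases were chosen because their removal raised |r|: 18 to 29%.

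**The case against.** The strongest reply is that nothing is wrong on the plan's own terms. SA1 and SA2 ask whether groups differ, SA3 asks about association, and unadjusted tests answer those questions. The supplement is exploratory and uses only baseline data. This stands, and it is why the planned tests should stay.

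Four stronger readings are tempting, and the documents do not support them.
- **That the t-tests carry a false-positive rate of up to 58%.** That figure is an error rate only for the equal-age question, which the plan does not pose, and only under the largest assumed gap and correlation.
- **That the protocol itself declares HRV dependent on age and gender.** The SDNN rule assigns individuals to an intervention and concerns one of seven measures. The pregnancy exclusion says nothing about age. Together they show that such characteristics were thought relevant, and no more.
- **That the case is equally strong for SA1.** No passage links age to caregiver reactions or caregiving involvement. The possible gain there is mainly mutual adjustment of race and gender.
- **That the planned correlations should be replaced.** The plan ties removal of influential cases to assumption violations. It does not clearly say that cases would be picked for their effect on r, although its wording for A2, about features that may reduce the coefficient, is ambiguous. The simulations show little inflation under most fixed rules, so they give no ground for substituting a rank correlation or otherwise altering A2.

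**Conclusion.** The point holds as an inexpensive improvement. It is best supported for SA2, plausible for SA3, and a matter of consistency for SA1. The planned results cannot separate a race or gender difference in HRV, or a stress-HRV association, from differences in age and gender, and the disparity and tailoring use in the Background makes that separation worth reporting.

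How much it would change is unknown. The 0 to 0.25 SD range for the race contrast rests wholly on assumed age gaps and correlations. The gender contrast depends in the same way on an age gap between men and women, which is also not given. The randomized comparison in A1 is untouched. The T1 HRV data are also unaffected by the COVID-19 remote-collection changes, which concern T2 and T3.

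**What to change.** Keep the t-tests and correlations as planned, and add beside them:

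1. **SA2:** for each HRV measure, one linear regression on race, gender and age, with spectral measures log-transformed where skewed. Report the race and gender coefficients with 95% CIs. The same model may be run for SA1 for consistency.
2. **SA3:** partial correlations given age and gender.
3. **Interpretation:** one sentence saying that the unadjusted result answers the marginal question and the adjusted one the question at equal age and gender.
4. **Sensitivity only:** health conditions and current medications, both collected at T1. They may lie on the path from race to HRV, since the Background reports worse physical health in African American caregivers.
5. **Minor:** wherever influential cases are removed from a planned correlation, also report the result with all cases.

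The cost is analysis-plan wording, with no new data. The drawbacks are longer reporting, two estimands to explain, and dependence on the regression model if the race groups overlap little in age.

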## Confidentiality of Data

1. To maintain the confidentiality of the data:  I will use a unique study identifier to code individuals' identifiable data and will store the master list separate from the study data..

**HRP-**

Other (please explain)

Provide a plan to destroy identifiers including how and when.

2. How are you storing your electronic data?  UH Redcap

CWRU Redcap  Secure Research Environment (SRE)

CWRU Box  OnCore  UH Secure Network Drive

CWRU Secure Network Drive  Other - List storage method

and provide justification:

3. Storage location of the paper research data and documents, if applicable:

Paper research data and documents will be stored in a double-locked secure environment in the following location:

*France Payne Bolton School of Nursing study office*

4. Will data be shared?

Yes

1. List the exact data elements that will be shared:

2. Describe how data will be sent:

No

N/A

*(Please note: if sharing data, please contact the UH Grants and Contracts Specialist or CWRU Tech Transfer Office to ensure the proper contracts/agreements are in place.)*

## **HIPAA Authorization**

Does this study collect, access, use, or distribute any Protected Health Information (PHI)?

Yes  No

If yes, indicate how HIPAA authorization will be obtained (check all that apply):

HIPAA authorization is in the consent form

Requesting a full or partial waiver of HIPAA for prescreening

I will complete the Request for Waiver of HIPAA

Authorization form. *See SpartaIRB Library*

Requesting a full or partial waiver of HIPAA

I will complete the Request for Waiver of HIPAA

Authorization form. *See SpartaIRB Library*

## **Devices**

This is **not** device study. The protocol is considered non-therapeutic (non-therapeutic is defined as research not intended to diagnose, prevent, cure, mitigate, treat, etc. a disease or condition) by the FDA. – *You may delete the rest of this section.*

OR

This is a device study. The protocol is considered therapeutic (research intended to diagnose, prevent, cure, mitigate, treat a disease or condition) by the FDA.

1. Is there an IDE (Investigational Device Exemption) for the proposed study?

Yes, provide an official letter of support or proof of approval which identifies the IDE holder and IDE number.

No

2. Is the device (and its use) a non-significant risk device for the proposed study design?

Yes

No

N/A

3. If the research involves device(s), describe your plans to use, store, handle, administer and track those device(s) to ensure that they will be used only on research participants and be used only by authorized investigators.

## Risks to Research Participants

1. List the reasonably foreseeable risks such as breach of confidentiality, discomforts, hazards, or inconveniences to the research participants related to their participation in the research. Include a description of the probability, magnitude, duration, and reversibility of the risks. Include the physical psychological, social, legal, and economic risks.

*No physical, psychological, social, legal, or economic risks other than associated with daily living, are expected for the caregiver who participates in this study. Thus, the risks for emotional/physical distress should be minimal. Several measures will be taken to minimize the potential risk for distress while completing study questionnaires, HRV measurement, or during the interventions that involve journaling about the use of education, resourcefulness skills or breathing techniques, or use of the biofeedback device. If a caregiver becomes upset during a data collection interview or intervention meeting or phone call/email/text, the team member will offer to end it immediately, provide emotional support and/or make a referral to a mental health professional as needed. It is possible that discussion of stresses related to having a family member with bipolar disorder may stimulate emotional responses in the caregiver during the 4 week interventions. All weekly phone call/email/text field notes will be stored in REDCap. In addition, there will be ongoing supervision by the intervention supervisor ([name]), who is an experienced, doctorally-prepared, advanced practice psychiatric nurse. The data collectors and interventionists will report adverse effects to [name] and PI [name] as soon as discovered.*

*In regard to the use of the HRV measuring instrument, there have been no reported safety risk with the use of this instrument thought participants may fear it. It has passed electromagnetic interference and compatibility tests. Thus, there is no danger of electric shock from use of the device. We let the individual know that the device is for research purposes only and not meant to be diagnostic, the data obtained from the device will record heart rhythm but will not give information about treatments needed for heart health. If the individual would like more information about heart health or risk, they will be encouraged to talk to their doctor.*

2. If applicable, indicate which experimental procedures may have risks to the research participants that are currently unforeseeable.

N/A

3. If applicable, describe the risks to others who are not research participants.

N/A

4. Describe the availability of medical or psychological resources that research participants might need.

N/A

